Rationale: Evidence-based treatments for posttraumatic stress disorder (PTSD), such as Eye Movement Desensitization and Reprocessing (EMDR) and Imagination and Rescripting Therapy (ImRs), are highly effective treatments in the majority of the PTSD patients. PTSD is highly comorbid with personality disorders (PD), especially borderline personality disorder (BPD), and cluster C - avoidant, dependent, or obsessive-compulsive - personality disorders (CPD). It is not clear yet what treatment is most effective for those who suffer from both PTSD and PD. There is growing motivation in clinicians to offer PTSD treatments to PTSD with comorbid PD, because these treatments are highly effective, relatively short (weekly sessions, 3-6 months) and there is some evidence that with PTSD treatment, comorbid PD symptoms might resolve as well. PTSD treatments are less time-consuming than PD treatments and - at least in the short term - financially attractive. However, at least 30-44% PTSD patients do not sufficiently respond to these treatments. Moreover, a high number of PTSD patients are excluded from these therapies because of suicidality, self-destructive behaviour or other personality problems. Therefore, it might be more efficient to add a PD treatment at the same time. Evidence-based treatments for personality disorders (PD), such as dialectical behaviour treatment (DBT) for BPD, and schema-focused treatment (SFT) for CPD are well established. These treatments are more intensive (twice a week for at least one year) than PTSD treatments. There is some evidence that integrated PTSDPD treatment is twice as effective on reducing PTSD symptoms than PD treatment alone, but integrated PTSD-PD treatment is not yet directly compared to PTSD treatment alone. This study will address this knowledge gap, including secondary outcome measures on functioning, quality of life and cost-effectiveness.

The result of this study might be that one or the other treatment works better, depending on the personal profile of the patient. So far, some psychological factors have been found

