For PTSD with comorbid (B)PD an integrated DBT-PTSD-treatment is investigated in 3 RCTs (Steil et al., 2011, Bohus et al., 2013, Harned et al., 2014). The first study showed moderate to large effect sizes of DBT-PTSD compared to waiting list, in terms of overall BPD severity (SMD -0.74 [95%CI -1.47 - -0.01]), depression (SMD -1.06 [95% CI -1.84 - -0.29]), and anxiety (SMD -0.96 [95% CI -1.72 - -0.20]) (Steil et al., 2011). The second study indicated that DBT-PTSD resulted in a greater mean change than waiting list on PTSD symptoms (CAPS 33.16 vs. 2.08), but not on BPD symptoms (Bohus et al., 2013). Integrated DBT-PTSD-treatment was also compared to DBT-alone, and led to larger and more stable improvements in PTSD symptoms, doubled remission rate (80% vs. 40%), and decreased suicide rates (2.4 times less likely) and self-injury (1.5 times less likely), with moderate to large effect sizes for dissociation, trauma-related guilt cognitions, shame, anxiety, depression, and global functioning in completers (Harned et al., 2014). However, integrated PTSD-PD treatment is not yet directly compared to PTSD treatment alone.

In summary, there is growing motivation in clinicians to offer PTSD treatments to PTSD with comorbid disorders, because these treatments are highly effective, relatively short, and there is some evidence that with PTSD treatment, comorbid PD symptoms might resolve as well. However, it may be more efficient to add a PD treatment at the same time. Evidence-based treatments for personality disorders (PD), such as dialectical behaviour treatment (DBT) for BPD, and schema-focused treatment (SFT) for CPD are well established. These treatments are more intensive (twice a week for at least one year) than PTSD treatments. There is some evidence that integrated PTSD-PD treatment works twice as good as PD treatment alone, but integrated PTSDPD treatment is not yet directly compared to PTSD treatment alone. This study will address this knowledge gap.

Hypotheses A: We hypothesize that in PTSD with comorbid PD it is more effective to provide integrated PTSD-PD-treatment compared to PTSD treatment alone, primarily in terms of response rate in PTSD symptoms. Secondly, we hypothesize that PD symptoms, disability and quality of life will improve and cost-effectiveness will be better with integrated treatment.

- A1. In patients with PTSD with BPD, integrated DBT-EMDR treatment results in a higher response rate than EMDR-only;

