3. STUDY DESIGN

The design of this study consists of two – connected - RCTs comparing PTSD-treatment to integrated PTSD-PD treatment in patients with PTSD and comorbid PD in a specialized treatment setting (figure 2):

A1. EMDR versus integrated DBT-EMDR, and

A2. ImRs versus integrated SFT- ImRs.

Assessment points are: baseline (T₀), after 3 months (T₁), after trauma treatment has finished, around 6 months (T₂), 3 months after T₂ (T₃), after 12 months (T₄) and at 18 months (follow-up, FU).

PTSD treatments specifically address the troubling memories of the traumatic event and the personal meaning of the event and consist of 12 to 18 sessions in maximum 6 months, and are:

- EMDR (Eye Movement Desensitization and Reprocessing)

EMDR was developed in 1987 by Shapiro (De Jongh & Ten Broeke, 1998). In EMDR the therapist induces a bilateral stimulation once the client has focused the attention on a disturbing image or memory related to the traumatic experience. The bilateral stimulation is induced by the movement of the therapist's fingers in front of the patients face from

the left to the right with the instruction for the client to follow this movement of the hand with the eyes. Attention is drawn to what traumatic memory and the dysfunctional thoughts about it are currently doing with the patient and not to what the patient was thinking during the traumatic experience.

- ImRs (Imagination and Rescripting Therapy) (Arntz et al., 2007, Raabe et al., 2015).

In ImRs, the patient imagines the (onset of a) traumatic experience and subsequently changes the original course of events by imagining different interventions and outcomes, thereby allowing for the change of original schematic representations and cognitions (Hackmann et al., 2011). ImRs implies changing the traumatic imagery in fantasy, to produce a more favourable outcome (without denying the trauma), imagining having control over the situation and being able to act according to one's needs, to express one's feelings and action tendencies. ImRs was hypothesized to alleviate PTSD symptoms as well as change trauma-related beliefs and schemas (e.g. powerlessness, victimization, and inherent badness). It is suggested that ImRs might be more effective in patients with emotions and cognitions like anger, irrational guilt, shame disgust and/or self-contempt (Arntz et al., 2007).

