Integrated PTSD-PD treatment consist of a PTSD treatment interwoven in a PD treatment that takes at least twice sessions per week, for the duration of one year:

- DBT (Dialectical Behavior Treatment), a manualized outpatient cognitive-behavioral treatment with two components: (a) weekly individual therapy and (b) weekly group skills training. Individual sessions focus on a hierarchy of target behaviors, which the patient tracks on a daily basis with diary cards. Behavioral analyses of the pattern and chain of thoughts, emotions, and events take place routinely to help the patient identify triggers and alternative strategies for coping. Change strategies such as problem solving and reinforcement techniques are used in combination with acceptance and validation of the patient's experience. Group skills' training is used to help patients develop less self-destructive and more adaptive means of coping with intolerable affects. These skills include awareness of emotions and reactions, interpersonal effectiveness, emotion regulation, and distress tolerance. Skills are then integrated into the individual treatment in problem situations, e.g. suicidal urges (Linehan, 1993).

- SFT (schema focused treatment) is a form of psychotherapy integrating cognitive therapy, behavior therapy, object relations, and gestalt therapy into one unified,

systematic approach to treatment. The focus in SFT is on changing maladaptive schemes that patients develop early in life and thereby improve emotion regulation skills. Change is achieved through a range of behavioral, cognitive, and experiential techniques that focus on (1) the therapeutic relationship, (2) daily life outside therapy (also through homework assignments), and (3) past (traumatic) experiences (Young et al., 2003). Psychomotor therapy (PMT) is part of the SFT treatment protocol.

[figure not shown]
In the Sinai Centrum, 2 “Zorgpaden” will be implemented in Fall2017:

“Zorgpad 1” with EMDR or ImRs (3-6 months) and Zorgpad 2” with EMDR-DBT or ImRs - SFT (9-12 months). Therapists need to be “adherent-to-the model”, which will be ascertained by regular supervision with audiovisual recordings based on the different theoretical psychotherapeutic principles and therapies are delivered by protocol. At this moment, there is no clear scientific evidence and criteria are not explicitly defined for the one or the other treatment, except that patients with PTSD without comorbid PD have to be indicated for “Zorgpad” 1.

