5.1.2 Secondary outcome parameters

○ Presence of PTSD (DSM-5) as measured with: CAPS-5 (Clinician Administered PTSD Scale, Weathers et

al., 2014, Boeschoten et al., 2014)

○ PCL-5 (PTSD Checklist for DSM-5; Weathers et al., 2013; Boeschoten et al., 2014; Bovin et al., 2016).

- Presence and severity of personality disorders as measured with the SCID-5-PD (Structured Interview for DSM-5 Personality Disorders; First et al 2016) to assess presence and severity (dimensional score) of the DSM-5 personality disorders
- Demographic questionnaire

- Outcome Questionnaire -45 (OQ-45), with 25 items on psychiatric symptoms and 20 on interpersonal, occupational and social functioning (de Jong et al., 2008)
- BDI (Beck Depression Inventory, Beck et al., 1988)
- AUDIT (Alcohol Use Disorders Identification Test, Babor et al., 2001) to assess alcohol and drug abuse
- SCID-5-S (American Psychiatric Association, 2017).
- WHODAS 2.0 (World Health Organization Disability Assessment Schedule, Ustun et al 2010)
- EQ-5D-5L (<http://www.euroqol.org/eq-5d-products/eq-5d-5l.html>) to measure quality-adjusted life year (QALY)
- Tic-P (Trimbos/iMTA questionnaire for costs associated with psychiatric illness) for health care consumption (Hakkaart-van Roijen et al., 2002)
- NSSI screening; Screeningsvragenlijst opzettelijk zelfverwondend gedrag (Baetens & Claes, 2014) to assess selfinjury.
- SMI-118 (Schema Mode Inventory 118 items, Young, Arntz, Atkinson, Lobbestael, Weishaar, Van Vreeswijk & Klokman, 2008).
- YSQ-75 (Young Schema Questionnaire 75 items, Young & Brown, 1998).
- The ITQ (International Trauma Questionnaire) assesses PTSD and complex PTSD (CPTSD) symptoms according to the diagnostic formulation published in the ICD-11 (Karatzias et al., 2016; Cloitre et al., 2018). Since the CAPS-5 will be used to assess PTSD in the current study, patients will be asked to only complete the CPTSD items of the ITQ. The ITQ measures CPTSD through six five-point Likert scale (0-4) items related to three symptom clusters of difficulties in emotion-regulation (C1-2), negative self-concept (C3-4) and disturbed relationships (C5-6). Additionally, three five-point Likert scale items assess functional impairment (social, occupational and other important areas of life) associated with CPTSD symptoms (C7-9). A diagnosis of CPTSD requires that criteria for a PTSD are met (as measured by the CAPS-5), as well as a

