7.2 Secondary study parameters

Secondary study parameters are quality of life with WHODAS, EQ-5D-5L, and health care consumption with Tic-P. The secondary analyses on these continuous measures will be similar to the primary analyses.

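### Better cost-effectiveness is hypothesised, but section 7.2 analyses costs and quality of life only separately, so a dearer-and-better result would leave the hypothesis open

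*Combined protocol and SAP*

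**What the plan says.** The Summary (Rationale) describes the study as "including secondary outcome measures on functioning, quality of life and cost-effectiveness". Hypotheses A in the Introduction give a direction: "cost-effectiveness will be better with integrated treatment".

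Section 5.1.2 lists the two instruments that an economic evaluation would need: "Tic-P (Trimbos/iMTA questionnaire for costs associated with psychiatric illness) for health care consumption", and EQ-5D-5L "to measure quality-adjusted life year (QALY". Table 1 schedules both at T0, T2, T4 and the 18-month follow-up.

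Section 7.2 is the only analysis text on them. It reads "Secondary study parameters are quality of life with WHODAS, EQ-5D-5L, and health care consumption with Tic-P", followed by "The secondary analyses on these continuous measures will be similar to the primary analyses". The primary analysis in section 7.1 is a linear mixed model for one outcome, with time, treatment, their interaction, covariates, a random intercept and an autoregressive residual structure.

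Nothing in section 7 mentions cost-effectiveness. The documents give no QALY derivation, unit costs, costing perspective, time horizon, cost-effectiveness ratio, net benefit or willingness-to-pay range, and they mention no separate health-economic plan.

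**The concern.** Cost-effectiveness relates the extra cost of one treatment to its extra effect. Two separate group comparisons answer two other questions: does the cost differ, and does quality of life differ? When one arm costs more and also does better, those answers do not say whether the gain is worth its price. That needs a willingness-to-pay value and an uncertainty statement that allows for costs and effects being correlated within patients.

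This matters here because integrated treatment is much more intensive by design, so the trade-off case is a realistic outcome. The perspective, horizon, unit costs and threshold range can each change the conclusion. If they are chosen after the data are seen, the result on a directional hypothesis is open to selection.

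**Working it through.** The plan states no economic figure, so there is nothing to reproduce. The check has three parts.

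**1. What the planned models can and cannot give.** With visits at 0, 6 and 12 months, the area under the utility curve by the trapezium rule is

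0.5 × (u0 + u2)/2 + 0.5 × (u2 + u4)/2 = 0.25·u0 + 0.5·u2 + 0.25·u4.

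A difference in mean QALYs is therefore a linear contrast of visit means from a model like that in section 7.1, and it has a standard error. This is crude, because T2 is tied to the end of trauma treatment and its date varies between patients. The plan does not specify the contrast. A separate cost model likewise gives mean differences. Neither model gives the correlation between a patient's costs and effects, and neither applies a willingness-to-pay value.

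**2. How different the treatment loads are.** Inputs from section 3: PTSD treatments "consist of 12 to 18 sessions in maximum 6 months"; the PD treatment in the integrated arms takes "at least twice sessions per week, for the duration of one year". The same section also describes the integrated care pathway as lasting 9 to 12 months. The two durations should be reconciled; both are used here.

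| Integrated duration | Sessions | Ratio to 18 | Ratio to 12 | Excess |
|---|---|---|---|---|
| 9 months (39 weeks) | 2 × 39 = 78 | 78/18 = 4.3 | 78/12 = 6.5 | 60 to 66 |
| 12 months (52 weeks) | 2 × 52 = 104 | 104/18 = 5.8 | 104/12 = 8.7 | 86 to 92 |

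The range is about 4.3 to 8.7 times as many contacts, assuming no missed weeks. It is not a cost ratio: one of the two weekly DBT components is a group session, and the documents give no unit costs.

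**3. What separate results leave open.** This illustration uses **assumed** values, none from the documents except 50 patients per arm (section 4.4): cost difference dC = 4000 with SD 8000; QALY difference dQ = 0.08 with SD 0.20.

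- SE of dC = 8000 × √(2/50) = 1600, so z = 2.5 and p = 0.012.
- SE of dQ = 0.20 × √(2/50) = 0.04, so z = 2.0 and p = 0.046.

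The separate analyses would say that integrated care is dearer and more effective. Incremental net benefit at willingness-to-pay λ is λ·dQ − dC, with variance λ²·SE_Q² + SE_C² − 2·λ·r·SE_Q·SE_C, where r is the cost-effect correlation.

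| λ | Net benefit | SE (r = −0.5) | SE (r = 0.5) | P(cost-effective), r = −0.5 | P(cost-effective), r = 0.5 |
|---|---|---|---|---|---|
| 20000 | 1600 − 4000 = −2400 | 2117 | 1386 | 0.128 | 0.042 |
| 50000 | 4000 − 4000 = 0 | 3124 | 1833 | 0.500 | 0.500 |
| 80000 | 6400 − 4000 = +2400 | 4233 | 2771 | 0.715 | 0.807 |

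Identical separate results fit a negative, zero or positive net benefit, depending on λ. At a fixed λ, the precision depends on r. The planned analyses supply neither.

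**The case against.** Several arguments on the other side have force.

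- *The models are not useless.* A reader might infer that separate mixed models can say nothing about QALYs or cost-effectiveness. That goes too far. A QALY contrast can be formed as shown, and if one arm is cheaper and better, or dearer and no better, separate results largely settle the direction. This stands, and it limits the gap to the trade-off case.
- *Higher cost is not a given.* A reader might infer from the session counts that the integrated arm must cost more in total. The documents do not support that. Tic-P covers health-care consumption generally. Section 3 allows crisis care, and it allows further treatment in the PTSD-only arms before T4 when the need is acute. No unit costs are stated. This stands.
- *Skewed costs.* A reader might object that normal errors suit cost data poorly. Section 7.2 says the analyses will be similar, which does not fix the error distribution, and the documents contain no cost data to test it. The point does not rest on this.
- *Scope.* Section 2 does not list cost-effectiveness as an objective, and the Summary endpoints and the questions in section 5.3 speak only of health costs, which section 7.2 does analyse. This shows that rewording is a legitimate remedy. It does not remove the mismatch, because the directional hypothesis remains in the Introduction.

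**Conclusion.** The concern holds in a limited form. A secondary hypothesis of better cost-effectiveness has no planned analysis that combines costs and effects, and it would be left open if integrated care proves both dearer and more effective. That case is plausible given about 4.3 to 8.7 times as many contacts, but it is not certain. The contact range assumes full attendance over 9 to 12 months. The net-benefit figures illustrate the mechanism under assumed values and do not predict this trial's result.

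A reader might go further and conclude that the hypothesis can be neither confirmed nor refuted under any outcome. The documents do not support that, because a dominance result could be read from the separate analyses. The primary CAPS-5 comparison is unaffected. This is a cheap improvement, not a threat to the trial's main conclusion.

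**What to change.** In section 7.2 add, for each RCT, a cost-utility analysis from T0 to T4:

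- **QALYs:** per patient, the area under EQ-5D-5L utility using actual assessment dates, adjusted for baseline utility.
- **Costs:** total per patient from Tic-P, with a stated rule for any interval that its recall period does not cover (the documents give no recall period). Add protocol therapy sessions from treatment records only where Tic-P does not already count them. The documents do not say that attended protocol sessions are logged per patient, so this needs confirming.
- **Result:** incremental net benefit over a stated willingness-to-pay range, with a bootstrap of patients' cost-QALY pairs.
- **Horizon:** T4 as the main horizon, because section 3 lets PTSD-only patients start SFT or DBT afterwards. Report 18 months as a sensitivity analysis, since that later treatment is arguably part of the cost of the PTSD-only strategy and both instruments are collected then.

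Otherwise, reword the Summary and Hypotheses A so that they promise only separate comparisons of costs and quality of life.

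The first option costs one extra secondary analysis and a choice of unit costs. It uses instruments and visits already scheduled, subject to the two data points above. The second costs a change of wording.

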7.3 Other study parameters

The analyses on other study parameters, including the AUDIT will also be similar to the primary and secondary analyses. Safety data: Incidences (number and % of subjects with at least one occurrence) of key SAEs and AEs will be presented per group. For exploratory purposes, confidence intervals comparing both groups will be provided.

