treatment (1.0), the number of persons needed to include is 50 persons per condition to reach for 80% power. Expecting a dropout rate of 25%, we will include 63 persons per arm, for 4 arms a total of 252 adult patients with PTSD and - at least 4 - PD symptoms. Of these patients, 80 next to 40 healthy matched controls will be asked for additional MRI research before and after treatment. In total, 292 persons will be included in this study.

Intervention: In patients with PTSD and BPD: EMDR (3-6 months plus 6-9 months treatment pause) compared to integrated DBT-EMDR (12 months); in patients with PTSD and CPD: ImRs (3-6 months plus 6-9 months treatment pause) compared to integrated ImRs-SFT (12 months).

Main study parameters/endpoints: Primary outcome measure is PTSD symptom severity after 12 months. Secondary outcome measures are PD symptoms (SCID-5-PD), disability (WHODAS), quality of life (EQ-5D-5L) and health costs (Tic-P). At baseline (T₀) and after 12 months (T₄) clinical interviews (CAPS-5, SCID-5-PD dimensional score) and self-rating scales (PCL-5) will be used. After 3 (T₁), 6 (T₂), 9 (T₃), and 18 months (follow-up), questionnaires only will be used. At baseline, candidate predictors will be measured including above mentioned cognitive, affective, relational factors, and hormonal and epigenetic factors. In a subgroup, structural and functional MRI, with resting-state and an emotion processing (face recognition) will be performed.

Nature and extent of the burden and risks associated with participation and benefits:

The burden and risks associated with participation in this study is reasonable. All patients will receive psychotherapy, which is considered to be the most effective treatment for PTSD and PD. There is evidence that all four conditions are therapeutic in patients with PTSD and PD and no evidence yet what condition is more effective. Total time of the six measurements is approximately 5 hours per patient for interviews and 5 hours for questionnaires (see table 3), which are partly part of the routine outcome measurements (ROM). Questionnaires can be filled in at home. On the one hand, extensive clinical interviews and self-rating scales can be felt as disturbing because of fatigue, taken time and emotional burden. On the other hand, patients may feel well recognized by the time taken by specialized clinicians for them. Assessors will be well-trained and work in close

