4.4 Sample size calculation

A power calculation was made based on Twisk (2007). We assume that PTSD treatment (EMDR or ImRs) have a small effect size (< 0.5) in the complex patient group with PTSD and comorbid

CPD/BPD, while the integrated treatment will show double effect sizes (1.0) (Harned et al., 2014). With a minimal clinical relevant difference of a 0.5SD on the CAPS-5, and the assumptions of a SD of 20.0, an intra-person correlation coefficient of 0.7, 5 follow-up measurements, the needed number to include is 50 persons per condition to reach for 80% power. Expecting a drop-out rate of 25%, we will include 63 persons per arm, or for 4 arms in total 252 persons.

In 2016, approximately 950 new patients were referred to the SC (Amstelveen). From these patients, ca. 450 had PTSD. From these PTSD patients, 168 had a comorbid PD and 188 more were not assessed for personality traits (“Uitgestelde diagnose”). We expect that introducing the assessment of axis II assessments with this study will result in an estimated 300 patients with PTSD and PD per year, and after 33% refusals or exclusions, in an estimated 200 patients possible to include per year. To be sure to include enough patients, we will need to include more patients from another site of the

Sinai Center, i.e. Amersfoort (400 patients, from which 216 PTSD patients, from which an estimated 100 PTSD + PD patients), and extend the inclusion period.

From these 252 patients, 80 will be asked for additional MRI, next to 40 healthy controls (Total sample size = 292). An estimated 40 patients will be available for a second MRI after 6 months (total of 160 scan sessions).

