6.2 AEs, SAEs and SUSARs

6.2.1 Adverse events (AEs)

Adverse events are defined as any undesirable experience occurring to a subject during the study, whether or not considered related to the study. All adverse events reported by the subject or observed by the investigator or his staff will be recorded.

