6.2.2. Serious adverse events (SAEs)

We do not expect any serious adverse event (i.e. any untoward medical occurrence or effect that results in death; is life threatening (at the time of the event); requires hospitalisation or prolongation of existing hospitalisation; results in persistent or significant disability or incapacity; is a congenital anomaly or birth defect; any other important medical event that may not result in death, be life threatening, or require hospitalization, may be considered a serious adverse experience when, based upon appropriate medical judgement, the event may jeopardize the subject or may require an intervention to prevent one of the outcomes listed above). The main reason for this is that all four treatments given in the RCTs are evidence-based for at least one of the disorders the patients suffer from (PTSD and PD) and patients who will be assigned to the PTSD-treatment only can given PD-treatment as well after T4 (after 6-12 months) within the research design.

Suicidality or self-injurious behaviour is very common in the study population included for this study. It is also known that starting a new treatment, such as EMDR or DBT could increase symptoms in the beginning, which can develop into suicidal behaviour. SAE's which will occur during the treatment and for which medical care is needed, will be reported to the accredited METC. To monitor the SAE's, patients will be asked to fill in a self-injury questionnaire (*Opzettelijk zelfverwondend gedrag, Baetens & Claes 2014 based on The Brief Non-Suicidal Self-Injury Assessment Tool (BNSSI-AT) van Janis Whitlock en Amanda Purington (2013)*) at the regular assessments. In case of SAE's for which medical care is needed, in between the assessments, therapists will report these incidents to the researchers at the weekly consultations, whom will report these to the accredited METC. The sponsor will report SAEs to the accredited METC that approved the protocol, within 7 days of first knowledge for SAEs that result in death or are life threatening followed by a period of maximum of 8 days to complete the initial preliminary report. All other SAEs will be reported within a period of maximum 15 days after the sponsor has first knowledge of the serious adverse events.

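### The planned AE/SAE comparison (% of subjects with at least one event) ignores repeat events and the time each patient was under event capture, which may differ between arms

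*Combined protocol and SAP*

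**What the plan says.** Section 7.3 gives the whole AE/SAE analysis in two sentences: "Incidences (number and % of subjects with at least one occurrence) of key SAEs and AEs will be presented per group", and "For exploratory purposes, confidence intervals comparing both groups will be provided". It does not state the scale, level or method of the intervals, or which events count as key. Section 7 plans no event counts, rates, person-time or time-to-event for safety.

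The other relevant statements are:

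- Section 6.2.2: "Suicidality or self-injurious behaviour is very common in the study population included for this study". It adds that a new treatment such as EMDR or DBT may worsen symptoms at first, and that this can lead to suicidal behaviour.
- Section 6.2.1: "All adverse events reported by the subject or observed by the investigator or his staff will be recorded".
- Section 6.2.2, on reporting: "SAE's which will occur during the treatment and for which medical care is needed, will be reported to the accredited METC". Between assessments, "therapists will report these incidents to the researchers at the weekly consultations".
- Summary, Intervention, for RCT A1: "EMDR (3-6 months plus 6-9 months treatment pause) compared to integrated DBT-EMDR (12 months". RCT A2 has the same pattern.
- Section 4.4: "Expecting a drop-out rate of 25%, we will include 63 persons per arm".
- Section 5.1.2 and Table 1: the NSSI self-injury screening is a secondary outcome parameter. Its row is marked at every time point from T0 to the 18-month follow-up (the T3 mark is a different symbol).

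**The concern.** Self-injury can happen many times to one patient. A yes/no summary counts a patient with one episode and a patient with twenty alike. If most patients have at least one episode, the percentage is near its ceiling and hardly responds when episodes become more frequent. If the extra episodes occur only in patients who already self-harm, it does not respond at all.

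The percentage also rises with the length of time over which events can be noticed. Therapists are the stated route for events between assessments, and therapist contact is planned to last much longer in the integrated arm. A difference in the percentage could then reflect length of capture instead of risk, and it would count against the integrated arm.

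There is no DSMB (section 6.5) and no interim analysis (section 7.4), so this end-of-study table is the only planned between-arm comparison of AEs and SAEs.

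**Working it through.** **Inputs.** The plan gives no figure for the safety comparison. From section 4.4: 63 per arm (50 × 1.25 = 62.5, rounded up). From the Summary: active treatment of 3-6 against 12 months. Event rates and dispersion are not in the documents and are assumed. The test level is assumed to be two-sided 5%.

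**Step 1: sensitivity to repeat events.** Let each patient have a negative binomial count with mean m and variance m + k·m².

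- P(at least one) = 1 − (1 + k·m)^(−1/k).
- Power for the percentage: Φ(|p2 − p1|/SE − 1.96), with SE² = [p1(1−p1) + p2(1−p2)]/63.
- Power for the rate ratio: Φ(ln(m2/m1)/SE − 1.96), with SE² = [(1/m1 + k) + (1/m2 + k)]/63.

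For k = 1 and m from 4 to 8:

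- p1 = 1 − 1/5 = 0.800 and p2 = 1 − 1/9 = 0.889. SE = √[(0.160 + 0.0988)/63] = 0.0641. 0.0889/0.0641 = 1.39, so power = Φ(−0.57) = 0.28.
- Rate ratio: SE = √[(1.25 + 1.125)/63] = 0.194. 0.693/0.194 = 3.57, so power = Φ(1.61) = 0.95.

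Other settings, each a true doubling:

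| Mean events | k | % with at least one | Power, % | Power, rate ratio |
|---|---|---|---|---|
| 4 to 8 | 0.5 | 88.9 to 96.0 | 33% | over 99% |
| 4 to 8 | 1 | 80.0 to 88.9 | 28% | 95% |
| 4 to 8 | 2 | 66.7 to 75.7 | 20% | 75% |
| 4 to 8 | 4 | 50.8 to 58.3 | 13% | 48% |
| 1 to 2 | 1 | 50.0 to 66.7 | 49% (47% with pooled variance) | 84% |
| 0.1 to 0.2 | 1 | 9.1 to 16.7 | 25% | 27% |

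With 63 × 0.75 = 47 patients per arm, the 4 to 8, k = 1 row becomes 22% against 87%. The advantage of rates is large for frequent events and disappears for rare ones.

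**Step 2: unequal capture, same true rate.** Take Poisson events at 1 per year in both arms, captured for 6 months in one arm and 12 in the other.

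- 6 months: 1 − e^(−0.5) = 39.3%.
- 12 months: 1 − e^(−1) = 63.2%.
- Difference 23.9 points, SE = √[(0.239 + 0.233)/63] = 0.086. The 95% interval is about 7 to 41 points, although there is no true difference.
- At 0.5 per year: 22.1% against 39.3%. At 2 per year: 63.2% against 86.5%.

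Simulation with 63 per arm, overdispersed counts (k = 1 to 2) and 0.1 to 4 events per year gave false differences of 4-17 points for 6 against 12 months (rejection 18-51%) and 7-33 points for 3 against 12 months (41-98%). A rate per person-time over the true capture window rejected in 2-7% of runs.

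**Step 3: is an offset enough?** Only if the rate is constant, and section 6.2.2 suggests it may not be. Suppose half of one expected yearly event falls in months 0-3 and the rest is spread evenly over months 3-12. Capture to month 6 sees 0.5 + 0.5 × 3/9 = 0.667 event in 0.5 year, or 1.33 per year. Capture to month 12 sees 1.00 per year. The rate ratio is 0.75 with no true difference, so the window itself must match, or results must be split by period.

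**The case against.** **A second self-injury comparison exists.** A reader might infer that a doubling of self-harm would go unseen in the whole trial. The documents do not support that. The NSSI is a repeated outcome, section 6.2.2 uses it for monitoring, and section 7.3 analyses other parameters in the same way as the primary outcome. This stands, with limits: section 7 never names the NSSI, nothing says it yields event counts, and sections 5.4 and 5.6 give priority to the PCL-5 and OQ-45 in drop-outs.

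**The event rate is assumed.** This stands. Very common carries no number, and SAEs needing medical care are a narrower and probably rarer set, for which Step 1 shows almost no gain.

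**Drop-out.** A reader might infer that 25% drop-out biases the comparison. Section 4.4 gives one overall figure, section 5.6 keeps treatment drop-outs in the study, and equal drop-out produced no bias in simulation (5-6% rejection). An invented split of 40% against 10% gave only 1-7 points. The route with support in the text is capture through therapists. Even that is a risk and not a stated fact: section 6.4 has SAEs reported to the end of the study, but does not say how they are found once therapy has ended.

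**Stakes and data.** The intervals are labelled exploratory and no safety test is planned, so power here only measures sensitivity. The protocol does not call self-harm its main risk, and section 6.2.2 expects no SAE. Section 6.2.1 promises that AEs are recorded, not that each act is a separate dated record. All of this stands and limits the point to a reporting improvement.

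**Conclusion.** The point holds as a moderate gap in the safety analysis. The AE/SAE comparison uses neither repeat events nor time under capture. If events number several per patient, a doubling shifts the percentage by about 7 to 9 points (4 to 8 events, k from 0.5 to 4), with 13-33% power against 48% to over 99% for a rate ratio. If events are rare, little is lost. If capture follows treatment contact, equal risk at 1 event per year could appear as about 39% against 63%. These sizes rest on assumed rates, on the assumed dispersion and, for the last, on capture ending with treatment in the PTSD-only arm. The documents do not establish that self-harm would go undetected, or that drop-out differs between arms. The primary result is not affected.

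**What to change.** In section 7.3, keep the number and % of subjects and add, within each RCT:

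- event counts and rates per person-month for self-injury/suicidal events, all AEs and all SAEs;
- an exploratory rate ratio with 95% CI from a negative binomial or robust Poisson model, with log time under event capture as offset. The date of last observation is not a substitute if capture stopped earlier;
- the same event source and the same window in both arms, or results also by period (for example months 0-6 and 6-12), because of Step 3;
- counts and person-time only, without a model, where events are few;
- a definition of the key events, and the NSSI named with its own analysis.

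The cost is a few lines of text, a little more analysis work, and event dates and capture end dates in the safety file. An offset does not correct for denser contact: integrated treatment has at least two sessions a week, so therapists may notice more in the same month. That is why the common source matters as much as the model.
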